### **EDSS, MSFC and SDMT**

For Expanded Disability Status Scale (EDSS), and its 7 functional system scores including Visual (Converted), Brainstem, Pyramidal, Cerebellar, Sensory, Bowel and Bladder (Converted), and Cerebral, each functional system score and EDSS total score will be summarized using descriptive statistics by treatment group.

For multiple sclerosis functional composite (MSFC), MSFC z-score [1] for T25FW, 9HPT and PASAT-3 will be derived as in Appendix 2 and will be summarized using descriptive statistics by treatment group.

The MSFC Z-score is calculated by creating Z-scores for each component of the MSFC, as explained below, and averaging them to create an overall composite score, i.e.,

MSFC Z-score = (Z25-foot-walk + Z9HPT + ZPASAT-3)/3, where Zj refers to Z-scores of component j.

A Z-score represents the number of standard deviations a subject's test result is higher (Z >0) or lower (Z <0) than the average test result (Z = 0) from the reference population. For this study, the reference population will be the subjects from Biogen 999MS005 MS COG norm healthy volunteer study.

For T25FW, 9HPT dominant hand, 9HPT non-dominant hand and PASAT-3, actual assessments as continuous variables will also be summarized using descriptive statistics by treatment group.

For Symbol Digit Mobility Test (SDMT), the SDMT scores will be summarized using descriptive statistics by treatment group .

### **MS Signs and Symptoms**

MS signs and symptoms are listed in 9 classes including Vision Problems, Cognitive Impairment, Coordination/Balance Problems, Bladder Dysfunction, Bowel Dysfunction, Sexual Function Problems, General Signs and Symptoms, Sensory Disturbances, and Motor Disturbances. The unlisted signs and symptoms are recorded under “Other Signs and Symptoms” in case report form (CRF).

Number and percentage of subjects having each listed MS signs and symptoms, and Other Signs and Symptoms will be displayed by treatment group.

[figure not shown]
### **Disease Activity by Brain MRI Metrics**

Disease activity is measured by consensus Gd lesion count, and T2 lesion volume.

[figure not shown]
The number of consensus GD-enhancing lesions and volume of T2 Lesions (in mL), and change from RENEW baseline of them at Day 1 in the current study will be summarized by treatment group.

[figure not shown]
Change from baseline of the number of Gd-enhancing lesions at Day 1 will be compared between treatment groups using a Wilcoxon signed-rank test.

[figure not shown]
Change from baseline of the volume of T2 lesions at Day 1 will be also compared between treatment groups using the Wilcoxon signed-rank test.

[figure not shown]

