5.5.2. Clinical Experience

As of 07 May 2015, 72 healthy volunteers (54 BIIB033 and 18 placebo) have been dosed in a single-ascending-dose (SAD) clinical study (Study 215HV101), 47 subjects with MS (32 BIIB033 and 15 placebo) have been dosed in a multiple-ascending-dose (MAD) clinical study (Study 215MS101), 82 subjects with AON (41 BIIB033 and 41 placebo) have been dosed in a Phase 2 Study 215ON201, and 418 subjects with MS (treatment groups still blinded) have been dosed in the ongoing Phase 2 Study 215MS201.

Overall, BIIB033 has been well tolerated in clinical studies. In the completed Study 215HV101 (SAD), which evaluated the safety, tolerability, and pharmacokinetics (PK) of BIIB033 in healthy volunteers, doses ranging from 0.1 to 100 mg/kg BIIB033 were administered to a total of 54 healthy adult volunteers. There were no serious adverse events (SAEs) in the SAD study. Most adverse events (AEs) considered related to study treatment in the SAD study were mild, except for 3 moderate events (2 cases of headache and 1 case of gastroenteritis). The most common AEs with an incidence of $\geq 5\%$ reported by subjects receiving BIIB033 were headache (10 subjects [19%]), upper respiratory tract infection (6 subjects [11%]), nasopharyngitis (4 subjects [7%]), and gastroenteritis (3 subjects [6%]). Overall, the frequency of AEs was similar between the BIIB033 and placebo groups.

In the completed Study 215MS101 (MAD), which evaluated the safety, tolerability, and PK of BIIB033 in subjects with RRMS or SPMS, multiple doses ranging from 0.3 to 100 mg/kg BIIB033 were administered to a total of 32 subjects. There were no SAEs in the MAD study. The frequency of AEs was similar in BIIB033-treated subjects compared with placebo-treated subjects. The most common AEs with an incidence of $\geq 5\%$ reported by subjects receiving BIIB033 were headache and urinary tract infection (5 subjects [16%] each), upper respiratory

CONFIDENTIAL

The information contained herein may not be used, disclosed, or published without the written consent of Biogen MA Inc.

tract infection and MS relapse (3 subjects [9%] each), and postlumbar puncture headache (2 subjects [6%]).

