### 3 STATISTICAL ANALYSIS METHODS

#### 3.1 General Considerations

Descriptive summary statistics will be presented for all study primary, secondary and [REDACTED] endpoints collected.

Unless stated otherwise, summary statistics will be presented by original treatment groups and overall. For continuous endpoints, the summary statistics will generally include number of subjects enrolled, number of subjects evaluated, mean, standard deviation, median, and range (minimum, maximum). For categorical endpoints, the summary statistics will generally include number of subjects enrolled, number of subjects evaluated, and the percent of subjects in each category.

Statistical testing for efficacy endpoints will be made between the BIIB033 group and the placebo group. There will be no multiple comparison adjustments.

Unless stated otherwise, all statistical tests will be 2-sided with statistical significance level of 0.05.

The statistical software, SAS®, will be used for all summaries and statistical analyses.

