### Treatment group

No study drug dosing is planned for this follow-up study. The treatment group used in the descriptive summary and treatment comparison is determined by the prior treatment with the investigational drug in 215ON201.

- new in 215ON203
  - baseline T2 volume in 215ON201 (0 and >0)
  - EDSS total score ( $\geq$ median and < median)
  - EDSS FS visual score ( $\geq$ median and < median)
  - RGCL thinning in the affected eye by week 4 ( $\geq$ median and < median)

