#### Analysis models

Analysis of covariance (ANCOVA) model will be used as the primary inferential analysis approach to evaluate changes from the baseline measurement in 215ON201 to Day 1 of 215ON203 in efficacy endpoints and to test the treatment differences between BIIB033 and placebo. ANCOVA model will include terms for the baseline value and treatment group. Based on Type III sum of squares, Least-squares (LS) adjusted mean of treatment difference, 95% confidence interval for the difference and the associated p-value will be presented.

Since this is a follow up study, due to loss of follow up, if the distribution of the responses is markedly non-normal (eg., highly skewed or contains outliers), the normality assumption appears dramatically violated, the Wilcoxon rank-sum test will be used to compare the treatment difference of efficacy endpoints. Normal probability plot, and QQ-plot with tests will be used to check normality assumption.

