## 5 SAMPLE SIZE DETERMINATION

The sample size is based on the number of subjects who participated in Study 215ON201 (approximately 82) rather than statistical considerations. The subjects eligible for this study must have participated in Study 215ON201.

[figure not shown]

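### Both MRI comparisons between arms name the Wilcoxon signed-rank test, a paired or one-sample test that cannot compare BIIB033 with placebo

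*SAP*

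**What the plan says.** SAP Section 3.3.3, under Disease Activity by Brain MRI Metrics, gives two testing rules. For lesion count: "Change from baseline of the number of Gd-enhancing lesions at Day 1 will be compared between treatment groups using a Wilcoxon signed-rank test". For lesion volume: "Change from baseline of the volume of T2 lesions at Day 1 will be also compared between treatment groups using the Wilcoxon signed-rank test".

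The rest of the SAP settles what is being compared. Section 3.1 states that "Statistical testing for efficacy endpoints will be made between the BIIB033 group and the placebo group", and on the grouping that "The treatment group used in the descriptive summary and treatment comparison is determined by the prior treatment with the investigational drug in 215ON201". Each subject therefore belongs to one arm only. Section 3.1 also sets the error rate: "all statistical tests will be 2-sided with statistical significance level of 0.05".

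Section 3.3.1 (Analysis models) makes ANCOVA the main inferential method. If normality is badly violated, "the Wilcoxon rank-sum test will be used to compare the treatment difference of efficacy endpoints".

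For brain MRI, Protocol Section 14.1.2.2 and the opening paragraph of SAP Section 3.3.3 mention only descriptive summaries. The tests are added in the MRI subsection of the SAP.

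**The concern.** The stated aim and the named test do not fit together. The aim is a contrast between two independent groups. The signed-rank test takes a single set of differences, either from one sample or from matched pairs, and asks whether they are centred on zero. It has no term for treatment arm.

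Common change over time is plausible here. Baseline precedes the first dose in Study 215ON201. Day 1 falls 2 to 3 years after Week 32 under the current protocol window. Since 32/52 is about 0.6 years, change from baseline spans roughly 2.6 to 3.6 years. If lesion counts or volumes drift alike in both arms, a signed-rank p-value labelled as a treatment comparison could be small with no treatment difference at all. If the arms moved in opposite directions, it could miss a real difference.

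Gd-enhancing lesion count and T2 volume are the only MRI measures listed under the secondary objective, and these are the only tests the visible text specifies for them.

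**Working it through.** **Inputs.** From the documents: two-sided alpha 0.05 (SAP 3.1), and at most 41 subjects per arm (Protocol 5.5.2: "82 subjects with AON (41 BIIB033 and 41 placebo) have been dosed in a Phase 2 Study 215ON201"). There is no planning figure to reproduce: "The sample size is based on the number of subjects who participated in Study 215ON201 (approximately 82) rather than statistical considerations". The documents give no MRI effect size, SD or retained arm size, so every shift, SD and arm size below 41 used here is an assumption.

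**Step 1: what each statistic can detect.** Let d_i be subject i's change from baseline and N the total number of subjects.

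- Signed-rank: W+ is the sum of the ranks of |d_i| over subjects with d_i > 0. Arm does not enter. Reassigning every arm label at random leaves W+ unchanged. Adding a constant c to every d_i does alter it.
- Rank-sum: W is the sum, over BIIB033 subjects, of the ranks of d_i among all N. Adding c to every d_i leaves W unchanged. Reassigning labels alters it.

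Applied to all the changes together, the first statistic therefore responds to common change and cannot use treatment; the second does the reverse. This needs no numerical assumption.

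**Step 2: the ways to follow the sentence literally.**

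1. *All changes together.* One p-value, for change over time.
2. *Each arm separately.* Two p-values for change over time, and no contrast between them.
3. *Paired across arms.* This needs matched pairs, which the plan does not define. With 41 and 38 subjects the calculation fails; with equal numbers the result would depend on an arbitrary matching.

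None of these tests BIIB033 against placebo.

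**Step 3: illustration, normal changes with SD 1, 3,000 simulated trials per row.** Monte Carlo standard error near 5% is √(0.05 × 0.95 / 3000) = 0.4 percentage points.

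| Per arm | Mean change, arm 1 / arm 2 | Signed-rank, all changes | Signed-rank, each arm | Rank-sum |
|---|---|---|---|---|
| 41 | 0 / 0 | 5.1% | 4.4%, 5.1% | 4.5% |
| 41 | +0.5 / +0.5 | 99.3% | 86.9%, 85.8% | 4.7% |
| 41 | +0.4 / −0.4 | 3.5% | 69.3%, 68.6% | 93.9% |
| 20 | 0 / 0 | 4.8% | 4.4%, 5.3% | 4.8% |
| 20 | +0.5 / +0.5 | 86.0% | 52.5%, 55.8% | 4.7% |
| 20 | +0.4 / −0.4 | 3.8% | 38.3%, 38.5% | 66.2% |

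Normal changes are a poor model for lesion counts, so a second run used Poisson counts whose mean falls from 1.0 to 0.4 in both arms (no arm difference). Signed-rank on all changes rejects 99.7% at 41 per arm and 87.8% at 20; rank-sum rejects 4.9% at both.

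**Step 4: how far this depends on the assumed shifts.** With 25 per arm, SD 1.5 and 4,000 trials per row:

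| Mean change, arm 1 / arm 2 | Arm difference | Signed-rank, all changes | Rank-sum |
|---|---|---|---|
| 0 / 0 | none | 5.2% | 4.3% |
| +0.1 / +0.1 | none | 7.1% | 5.1% |
| +0.5 / +0.5 | none | 61% | 4.9% |
| −0.6 / +0.6 | 1.2 (0.8 SD) | 3.3% | 77% |
| 0 / +1.2 | 1.2 (0.8 SD) | 72% | 77% |

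With little common drift, false positives stay near 5%. With an effect in one arm only, the two tests reject about equally often. The large gaps need a substantial common change, or arm effects that nearly cancel.

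**The case against.** The strongest reply is that this is a naming slip with an obvious reading. Both sentences say the comparison is between treatment groups, Section 3.1 fixes the contrast, and Section 3.3.1 already names the rank-sum test. A programmer who kept the treatment variable would arrive at rank-sum, and reporting a one-sample result as a treatment difference would take a further error. The two sentences are adjacent and nearly identical, so the repetition may be one slip copied. All of that is reasonable, and a misnamed test is the likeliest explanation. It does not rescue the text. A programmer must either follow the plan and produce a p-value for another question, or depart from it. Appendix 1 is headed as example SAS code for Sections 3.3.1 and 3.3.3, but no code is visible in this copy, so what would be run cannot be confirmed.

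Three further objections stand as limits:

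- The simulation shifts are invented, and the rows with large gaps are unfavourable cases (Step 4).
- Section 3.3.1 names rank-sum as a conditional fallback behind ANCOVA, while the MRI rule is specific to its endpoints. The two passages are inconsistent in the test they choose for the same kind of contrast, but not in direct contradiction.
- These are two secondary endpoints with no power basis and no multiplicity control. The descriptive MRI summaries by arm remain valid.

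**Conclusion.** The point holds. As written, the test named for both MRI endpoints cannot compare BIIB033 with placebo. That follows from the definition of the signed-rank statistic and the independence of the arms, and rests on no assumed effect size.

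The size of the error does rest on assumptions. Taking all changes together, false positives range from about 5% with no common drift to 99.3% with a 0.5 SD drift at 41 per arm, while rank-sum stays between 4.3% and 5.1% throughout. Rejection of a true 0.8 SD difference ranges from about 3% when the arm effects cancel to 72% when one arm alone changes (25 per arm, against 77% for rank-sum).

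The impact is confined to the p-values for Gd-enhancing lesion count and T2 lesion volume. The primary analysis is not touched. The text should be corrected before those tests are run.

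**What to change.** In SAP Section 3.3.3, Disease Activity by Brain MRI Metrics, replace signed-rank with rank-sum in both sentences. That matches the nonparametric test between arms already named in Section 3.3.1. Check that any MRI code in Appendix 1 and the analysis programs run a two-sample test with treatment as the class variable.

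Optionally, for T2 volume, a rank ANCOVA on baseline T2 volume could be specified, since the baseline value is already needed for the change score. The correction does not depend on it.

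The cost is one changed term in each of two sentences and a code check. No new data are needed.

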6. STUDY OBJECTIVES AND ENDPOINTS

6.1. Primary Objective and Endpoint

The primary objective of the study is to assess FF-VEP latency in subjects who were enrolled in Study 215ON201 at 2 years (+ up to 12 months) after the last study visit.

The primary endpoint that is related to this objective is the change in FF-VEP latency of the affected eye as compared to the baseline of the fellow eye at 2 years (+ up to 12 months) after the last study visit assessment (Week 32 or the projected Week 32 visit) in Study 215ON201.

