#### Baseline data

Unless stated otherwise, baseline data are defined as the data collected prior to the time and/or on the date of first dose in 215ON201. If there are more than one value on or before

the date of first dose, the non-missing value closest to and prior to (including on) the date of first dose will be used as the baseline value.

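### Both MRI treatment comparisons in SAP 3.3.3 test raw change from the pre-dose scan with no baseline adjustment, which can cost power on Gd lesions and lets part of any baseline imbalance into the contrast

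*SAP*

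**What the plan says.** SAP 3.3.3, Disease Activity by Brain MRI Metrics, sets two between-arm tests: "Change from baseline of the number of Gd-enhancing lesions at Day 1 will be compared between treatment groups", by a Wilcoxon signed-rank test, and "Change from baseline of the volume of T2 lesions at Day 1 will be also compared between treatment groups using the Wilcoxon signed-rank test". Neither sentence names a covariate or stratum. In the readable text of 3.3.3 these are the only secondary endpoints with a named between-arm test.

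SAP 3.1 fixes the reference scan: "baseline data are defined as the data collected prior to the time and/or on the date of first dose in 215ON201".

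SAP 3.3.1 makes ANCOVA the primary inferential approach for change in efficacy endpoints: "ANCOVA model will include terms for the baseline value and treatment group". If responses prove markedly non-normal, it falls back on a Wilcoxon rank-sum test and names no covariate for that either. The same section makes the per-protocol population primary.

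Protocol 6.1 (version 4.0) places Day 1 "at 2 years (+ up to 12 months) after the last study visit assessment (Week 32 or the projected Week 32 visit"). SAP 1.1 still carries a window of 2 years plus 4 months.

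**The concern.** The Gd count before dosing and the count on a scan more than two and a half years later may be only weakly related. If so, subtracting the first from the second adds the baseline noise to the outcome instead of removing it. A rank test on that difference then loses power, in a cohort capped at 82 that cannot be enlarged.

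A difference between arms in baseline Gd count also enters the change contrast with the opposite sign. Adjustment for the baseline value, which the SAP applies elsewhere and which needs no new data, removes most of both problems.

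**Working it through.** The plan gives no MRI power, lesion counts, SDs or baseline-to-Day 1 correlation, so there is no figure to reproduce. Everything below except step 1 rests on assumed inputs. Because a signed-rank test does not compare two independent groups, the planned test is represented by a two-sample rank-sum test on raw change.

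**1. Interval between scans.** Week 32 is 224 days, and 224/365.25 = 0.61 years.
- Earliest: 0.61 + 2 = 2.61 years.
- Latest under the SAP window: 0.61 + 2.33 = 2.95 years (rounded).
- Latest under protocol 4.0: 0.61 + 3 = 3.61 years.

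**2. Normal approximation.** Let r be the baseline-to-Day 1 correlation and k the baseline SD divided by the Day 1 SD.
- Variance of change: 1 + k² − 2rk. Variance after adjustment: 1 − r². With k = 1 the ratio V of the two is 2/(1 + r).
- If the adjusted analysis has 80% power, raw change has Φ((1.960 + 0.842)/√V − 1.960).

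| k | r | V | Power of raw change |
|---|---|---|---|
| 1 | 0 | 2.00 | Φ(0.02) = 51% |
| 1 | 0.5 | 1.33 | Φ(0.47) = 68% |
| 1 | 0.9 | 1.05 | Φ(0.77) = 78% |
| 1.5 | 0 | 3.25 | Φ(−0.41) = 34% |
| 1.5 | 0.5 | 2.33 | Φ(−0.13) = 45% |

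**3. Gd counts by simulation.** Assumptions: negative binomial with dispersion 0.5, Day 1 placebo mean 1, two-sided 0.05. The comparator is rank ANCOVA (Quade) of the Day 1 count on the baseline count. Correlations are on the count scale.

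| Per arm | Baseline mean | Rate ratio | Correlation | Raw change | Adjusted | Power ratio |
|---|---|---|---|---|---|---|
| 41 | 1 | 0.4 | 0 | 22% | 45% | 0.49 |
| 41 | 1 | 0.4 | 0.2 | 27% | 46% | 0.59 |
| 41 | 1 | 0.4 | 0.45 | 38% | 52% | 0.73 |
| 41 | 1 | 0.4 | 0.77 | 77% | 81% | 0.95 |
| 41 | 1 | 0.2 | 0 | 43% | 84% | 0.51 |
| 41 | 2 | 0.4 | 0 | 17% | 45% | 0.38 |
| 25 | 1 | 0.4 | 0 | 15% | 30% | 0.50 |
| 25 | 2 | 0.2 | 0.71 | 21% | 77% | 0.27 |
| 25 | 0.3 | 0.2 | 0 | 46% | 63% | 0.73 |
| 25 | 0.3 | 0.2 | 0.47 | 70% | 70% | 1.00 |

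Two things drive the loss: low correlation, and baseline counts above Day 1 counts. With low baseline counts it is smaller, and at moderate correlation it disappears.

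Adjusting the change itself works as well. With 25 per arm, baseline mean 1 and rate ratio 0.2, rank ANCOVA of the change had 59% power against 29% unadjusted at correlation 0, and 64% against 31% at 0.19.

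**4. Baseline imbalance.** Null simulation with 41 per arm and mean 1 at both times. The correlation here is that of the underlying normal copula.

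| Correlation | Share of baseline difference entering the change contrast, sign reversed | Type I error, all trials | Type I error, worst fifth by imbalance: raw change | Same fifth: adjusted |
|---|---|---|---|---|
| 0 | 1.00 | 5.1% | 16% | 4.6% |
| 0.3 | 0.77 | 5.1% | 13% | 4.5% |
| 0.6 | 0.49 | 5.1% | 11% | 4.4% |
| 0.9 | 0.15 | 5.2% | 7% | 4.9% |

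**5. T2 volume.** With 30% of subjects at zero volume at baseline, power was 21% for raw change against 27% adjusted in one scenario, and 30% against 38% in another (25 per arm). With lognormal volumes and 41 per arm it was 63% against 79% at log-scale correlation 0.80, and 73% against 85% at 0.95. In the lognormal runs part of the gain comes from analysing log volume rather than raw mL.

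**The case against.** **The effect may be too small for this to matter.** BIIB033 is presented as a remyelinating agent and dosing stopped at Week 20, so nothing in the documents predicts a large Gd effect years later. With 25 per arm, baseline mean 0.5 to 1.0 and correlation 0 to about 0.4, power for raw change against adjusted was 6–7% against 6–8% at rate ratio 0.8, 7–9% against 7–10% at 0.7, 9–18% against 18–21% at 0.5, and 26–54% against 62–70% at 0.2. This stands: below a large effect, neither analysis is useful.

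**An unadjusted rank test is the SAP's own fallback.** True, and sparse counts and skewed volumes are the likely case for it. But the fallback applies only once marked non-normality is seen, whereas the MRI text specifies its tests outright. The fallback also has the same weakness.

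**Change is the defined endpoint.** SAP 1.2 and protocol 6.2 do define it so. Adjusting the change for baseline keeps that endpoint.

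**Stakes are limited.** Protocol 14.1.2.2 plans only descriptive MRI summaries, and no multiplicity control is planned. This lowers the priority.

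**Text is missing.** The Appendix 1 code and some material around the MRI paragraph are not shown, so an adjustment there cannot be excluded; the two MRI sentences are nevertheless complete as they stand. The list item "baseline T2 volume in 215ON201 (0 and >0") under Treatment group in SAP 3.1 has lost its introduction, so it does not show how baseline T2 volume was meant to be used.

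**Stronger readings that the documents do not support.** A reader might infer that the tests give false positives, that power is halved as a matter of fact, or that the Gd result would mainly reflect who had enhancing lesions before dosing. The first fails because average type I error is about 5%. The other two need low correlation or high baseline counts, which the documents neither state nor exclude.

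**Conclusion.** The point holds in a conditional form. As written, both MRI comparisons use raw change without the baseline term that SAP 3.3.1 makes standard, and no reason is given.

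For Gd lesions the power ratio against an adjusted analysis runs from about half or less (correlation near zero, or baseline counts above Day 1 counts), through about 0.7 at correlation 0.45, to almost 1 at high correlation with equal means or at moderate correlation with low baseline counts. These figures rest on assumed negative binomial counts, and the absolute gain matters only for a large Gd effect. For T2 volume the gain is modest.

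The test is valid on average over randomisation, but its result is distorted given the imbalance actually seen. A baseline difference passes through in full only at zero correlation. The primary analysis set is also the per-protocol subset of subjects who returned, selected after randomisation, so imbalance there need not be chance alone.

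The scans are 2.6 to about 2.95 years apart under the SAP window. The figure of 3.6 years applies only under protocol version 4.0. Priority is low to moderate.

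**What to change.** Rewrite the two test sentences in SAP 3.3.3 before MRI data are compared by arm.

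- **Gd count and T2 volume:** keep change from the 215ON201 baseline as the endpoint and compare arms by rank ANCOVA (Quade). Rank the change and the baseline value over both arms together, regress the first ranks on the second, and compare the residuals between arms, two-sided at 0.05.
- **Gd sensitivity analysis:** van Elteren test of the Day 1 count, stratified by baseline Gd count 0 versus 1 or more.
- **Named test:** this wording replaces the signed-rank test. Correcting the name to rank-sum alone would leave the missing adjustment in place.
- **Window:** reconcile the follow-up window in the SAP with protocol version 4.0.

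The cost is two sentences and one program, with no new data. The downside is a statistic less familiar than a Wilcoxon test and without an effect estimate in lesions or mL, so the planned descriptive summaries of change by arm should stay beside it.
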